Individuals who have been enrolled in the study may be enrolled into the study up to two more times during the 12 months study period only if a minimum period of 28 days (4 weeks) has elapsed following their last dose of prophylaxis. Thus they can be enrolled in the study a maximum of three times. If an individual is enrolled again in this way, they will be re-randomised following the same procedure as enrolment.

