9.2.1 Proportions

These will be compared using chi squared or Fisher's exact test, as appropriate. Crude proportions will be calculated with the exact 95% confidence intervals (CI), where relevant.

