4.3 ANALYSIS OF PRIMARY OUTCOME

Primary objective:

To compare the efficacy of the ACT artemether-lumefantrine versus a multivitamin preparation as defined by the 28-day PCR parasite positivity rate or incidence of confirmed clinical malaria of any species

Primary endpoints:

Composite endpoint

- 1. 28-day PCR Plasmodium positivity rate of any species or
- 2. Proportion of participants with confirmed clinical malaria of any species reported between day 0 and day 28

The main analysis strategy for the primary outcome will be the intention-to-treat (ITT) principle followed by the per protocol (PP) analysis. Thus, we will first analyse the ITT population in which all participants recruited in the trial will be included in the analysis according to the randomisation arm irrespective of what they actually got. These ITT analyses will be followed by the analysis of the per protocol (PP) population in which, participants who did not adhere to the protocol will be excluded from analysis.

The efficacy of the ACT artemether-lumefantrine versus a multivitamin preparation as defined by the 28-day PCR parasite positivity rate or incidence of confirmed clinical malaria analysis in each arm will be summarised using proportions and the 95% confidence intervals. Crude proportions will be calculated with the exact binomial 95% confidence intervals. The risks differences in efficacy between AL and multivitamin will be reported along with the corresponding 95% confidence intervals. The robust standard error will be used to adjust for intracluster correlation of episodes from the same individual. The mixed effects Poisson/negative binomial regression model will be used to model the adjusted incidence rate ratios (IRR). The mixed effects models will take into account the correlation of multiple episodes from same participant.

Tests of significance will be performed at 5% significance level.

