# 4.3.2 Comparison of the efficacy of the ACT artemether-lumefantrine versus a multivitamin preparation as defined by the 28-day, 56-day, 84-day PCR parasite positivity rate or incidence of confirmed clinical malaria of any species

The efficacy of the artemether-lumefantrine versus a multivitamin as defined by the 28-day PCR parasite positivity rate or incidence of confirmed clinical malaria reported between day 0 and day 28 of any species from all follow-up months and for each follow-up month (day 28, day 56 and day 84) will be compared and presented in table 2 below.

	Efficacy rate, n	(%)	Risks difference/Incidence rate ratio (95% CI)	p-value
	AL (N=XXX)	Multivitamin (N=XXX)		
All months	XX (XX.X)	XX (XX.X)	XX.X (XX.X - XX.X)	X.XXX
Month 1	XX (XX.X)	XX (XX.X)	XX.X (XX.X - XX.X)	X.XXX
Month 2	XX (XX.X)	XX (XX.X)	XX.X (XX.X - XX.X)	X.XXX
Month 3	XX (XX.X)	XX (XX.X)	XX.X (XX.X - XX.X)	X.XXX

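### The exact binomial intervals planned for each arm's primary proportion ignore repeat records from one person and will be too narrow if within-person correlation is appreciable and repeats are common

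*SAP*

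**What the plan says.** SAP 4.3 says that the primary outcome "in each arm will be summarised using proportions and the 95% confidence intervals", and then names the method: "Crude proportions will be calculated with the exact binomial 95% confidence intervals". Next come the risk difference between arms and this sentence: "The robust standard error will be used to adjust for intracluster correlation of episodes from the same individual". For the incidence rate ratio, "The mixed effects models will take into account the correlation of multiple episodes from same participant".

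Repeat records arise in two ways.

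- **Visits within an enrolment.** Protocol 6.6 and 6.13 allow up to three follow-up visits over 84 days, all under the allocation given at enrolment.
- **Repeat enrolments.** Protocol 6.6 also allows re-enrolment: "Thus they can be enrolled in the study a maximum of three times". On each re-enrolment "they will be re-randomised following the same procedure as enrolment", so one person's enrolments may fall in different arms.

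SAP 4.3.2 reports an 'All months' row and a separate row for each month.

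**The concern.** An exact binomial interval takes its width from the number of records alone. If two records from one person tend to agree, they carry less information than two records from different people, and the stated 95% is not reached.

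The documents give reason to expect some agreement. Under Protocol 5.5.3 only malaria with symptoms confirmed by rapid test excludes a person, so a symptom-free PCR carrier can be enrolled. Under Protocol 6.8.1 PCR results return after about 3 to 6 months and do not guide treatment at the time of testing. A carrier can therefore be positive at more than one visit in the same arm. Protocol 6.6 itself plans genotyping to identify persistent infections.

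What is at stake is the precision claimed for each arm's positivity, which SAP 4.3 commits to reporting. The comparison between arms is not at stake.

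**Working it through.** **1. The plan's own figure.** The plan gives no figure for the arm intervals. Its sample size (SAP 2.5) supplies the rates: 5% on multivitamin and 3% on artemether-lumefantrine, with 80% power and 5% significance, taken as two-sided. The standard two-proportion formula with pooled variance gives 1,506 per arm. With the continuity correction, n/4 × [1 + √(1 + 4/(n × 0.02))]² = 376.5 × (1 + 1.0643)² ≈ 1,604.4, which rounds up to the stated 1,605. That number is for independent records. The 595 added per arm cover repeats and losses together, and no ICC or design effect is stated.

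**2. The planned interval.** With 2,200 records per arm:

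- multivitamin, 5% = 110 positive: exact 95% interval 4.13% to 6.00%
- artemether-lumefantrine, 3% = 66 positive: exact 95% interval 2.33% to 3.80%

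These are 2.6% and 3.4% wider than the simple normal interval. The exact method therefore absorbs a design effect of about 1.026² = 1.05 to 1.034² = 1.07 before coverage drops below 95%.

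**3. Design effect.** With m records per person in an arm, DE = 1 + (E[m²]/E[m] − 1) × ICC, and the correct width is √DE times the planned one. Two illustrative mixes of 1, 2 and 3 records per person (assumptions):

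- 60%, 25%, 15%: E[m] = 1.55, E[m²] = 2.95, so the bracket is 2.95/1.55 − 1 = 0.903
- 20%, 30%, 50%: E[m] = 2.3, E[m²] = 5.9, so the bracket is 5.9/2.3 − 1 = 1.565

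**4. Coverage of the unadjusted exact interval.** Beta-binomial simulation with 1,980 records per arm (2,200 less the 10% loss in Protocol 9.1) and rates of 3% and 5%:

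| Mean records | ICC | DE | √DE | Coverage |
|---|---|---|---|---|
| 1.55 | 0.1 | 1.09 | 1.04 | about 94–95% |
| 1.55 | 0.4 | 1.36 | 1.17 | about 91–92% |
| 2.3 | 0.1 | 1.16 | 1.08 | about 94–95% |
| 2.3 | 0.4 | 1.63 | 1.28 | about 88–90% |

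Under independence coverage is about 96%. A separate simulation with exactly three records per person and 2,200 records gives 93.7% at ICC 0.1 and 89.3% at ICC 0.3 (5% rate).

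**5. In percentage points.** Recomputing the exact interval at an effective sample size of 2,200/1.63 gives 3.90% to 6.30% for multivitamin (planned 4.13% to 6.00%) and 2.16% to 4.06% for artemether-lumefantrine (planned 2.33% to 3.80%). At DE 1.09 the multivitamin interval is 4.09% to 6.04%, barely changed.

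**The case against.** **The trial's conclusion is already protected.** This stands. The objective is a comparison, and the risk difference and incidence rate ratio are planned with the correlation allowed for. A reader might infer that the efficacy result is unsafe, and the documents do not support that. One could also argue that the robust-error sentence covers the arm proportions, since it names no quantity. But an exact binomial interval uses no standard error, so on that reading the paragraph contradicts itself and still needs an edit.

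**The intervals are labelled crude.** The word tells the reader that no adjustment was made. It does not make the stated 95% correct.

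**The size is assumed.** This stands too. A reader might infer that the intervals are certainly too narrow. With an average of 1.5 records per person and an ICC up to 0.1, the slack in the exact method keeps coverage at about 95% or above.

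**Nine records per person is not the normal case.** A reader might multiply three enrolments by three visits. With nine records for everyone, coverage would fall to about 87% at ICC 0.1 and 72% at ICC 0.3. That requires every person to attend every visit and to have all three enrolments in one arm. Under independent 1:1 allocation the latter has probability 2 × (1/2)³ = 1/4 even among those who enrol three times. A single-month row holds one result per enrolment, hence at most three per person. The 'All months' row may not stack visits at all, because SAP 2.2 can be read as positive at any follow-up.

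**The table shells print no arm-level interval.** Tables 2 and 3 show n (%) per arm and an interval only for the risk difference or rate ratio. A mismatch of intervals side by side in those tables therefore cannot be claimed. The text of SAP 4.3 still commits to the arm intervals.

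**Two extensions are not supported.** Protocol 9.2.1 says of proportions: "These will be compared using chi squared or Fisher's exact test, as appropriate". A reader might conclude that the p-values in Tables 3 to 5 carry the same fault. But Protocol 9.2 calls itself a brief overview and defers to the SAP, Table 3 shares the risk difference and rate ratio columns of Table 2, Table 5 is presented descriptively, and Tables 4 and 5 simply name no test. Nor does SAP 4.4.2 say that arm-specific positivity or its interval feeds the transmission model.

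**Conclusion.** The point holds in conditional form. SAP 4.3 names, for the arm-level primary proportions, an interval that cannot reflect the within-person correlation that the same paragraph recognises. If that correlation is positive and repeats are common, the intervals are too narrow. Over the assumed range (ICC 0.1 to 0.4, mean 1.55 to 2.3 records per person in an arm) the loss runs from essentially none to about seven percentage points of coverage. The pooled 'All months' result is the most exposed, provided that it stacks visits. This is a fault in descriptive reporting. It is worth correcting before analysis because the rule is explicit and the correction is cheap.

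**What to change.** Replace the sentence on crude proportions in SAP 4.3 with wording such as: *Arm-level proportions will be reported with 95% confidence intervals computed on the logit scale, with standard errors clustered on participant across all enrolments and visits in that arm. In rows with few or no events the exact binomial interval will be given and labelled as unadjusted for clustering.*

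The number of events below which the second rule applies should be fixed before the data are analysed. The fallback is needed because the logit interval cannot be computed with zero events, and a clustering estimate from very few events is unstable. Both situations are plausible in the species-by-month rows. Clustering on participant is suitable whether the 'All months' row stacks visits or counts each enrolment once.

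The cost is one SAP sentence and a small change to the analysis code. Intervals become slightly wider where correlation is present, and sparse rows keep an interval whose limitation is stated. The sample size and the planned between-arm analyses do not change.

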#### 4.3.1 Handling of missing data

For analyses of proportions, missing outcome will be imputed using plausible values. For example, the worst case scenario may be deemed appropriate but in that case sensitivity analysis would be done with the best case scenario.

# 4.3.2 Comparison of the efficacy of the ACT artemether-lumefantrine versus a multivitamin preparation as defined by the 28-day, 56-day, 84-day PCR parasite positivity rate or incidence of confirmed clinical malaria of any species

The efficacy of the artemether-lumefantrine versus a multivitamin as defined by the 28-day PCR parasite positivity rate or incidence of confirmed clinical malaria reported between day 0 and day 28 of any species from all follow-up months and for each follow-up month (day 28, day 56 and day 84) will be compared and presented in table 2 below.

	Efficacy rate, n	(%)	Risks difference/Incidence rate ratio (95% CI)	p-value
	AL (N=XXX)	Multivitamin (N=XXX)		
All months	XX (XX.X)	XX (XX.X)	XX.X (XX.X - XX.X)	X.XXX
Month 1	XX (XX.X)	XX (XX.X)	XX.X (XX.X - XX.X)	X.XXX
Month 2	XX (XX.X)	XX (XX.X)	XX.X (XX.X - XX.X)	X.XXX
Month 3	XX (XX.X)	XX (XX.X)	XX.X (XX.X - XX.X)	X.XXX

## Table 2 Comparison of efficacy of the ACT artemether-lumefantrine versus a multivitamin preparation as defined by the 28-day PCR parasite positivity or confirmed clinical malaria of any species

#### 4.4 ANALYSIS OF SECONDARY OUTCOMES

# 4.4.1 Comparison of the efficacy of the ACT artemether-lumefantrine versus a multivitamin preparation As defined by the 28-day PCR parasite positivity or confirmed clinical malaria for each species

The efficacy of the artemether-lumefantrine versus a multivitamin as defined by the 28-day PCR parasite positivity rate and incidence of confirmed clinical malaria reported between day 0 and day 28 for each species from all follow-up months and for each follow-up month (day28, day 56 and day 84) will be compared and presented in table 3 below.

## Table 3 Comparison of efficacy of the ACT artemether-lumefantrine versus a multivitamin preparation as defined by the 28-day PCR parasite positivity or confirmed clinical malaria for each species

	Efficacy rate, n (%)		Risks difference/Incidence rate ratio (95% CI)	p-value	
	AL (N=XXX)	Multivitamin (N=XXX)	_		
P. faciparum					
All months	XX (XX.X)	XX (XX.X)	XX.X (XX.X - XX.X)	X.XXX	
Month 1	XX (XX.X)	XX (XX.X)	XX.X (XX.X - XX.X)	X.XXX	
Month 2	XX (XX.X)	XX (XX.X)	XX.X (XX.X - XX.X)	X.XXX	
Month 3	XX (XX.X)	XX (XX.X)	XX.X (XX.X - XX.X)	X.XXX	
P. vivax					
All months	XX (XX.X)	XX (XX.X)	XX.X (XX.X - XX.X)	X.XXX	
Month 1	XX (XX.X)	XX (XX.X)	XX.X (XX.X - XX.X)	X.XXX	
Month 2	XX (XX.X)	XX (XX.X)	XX.X (XX.X - XX.X)	X.XXX	
Month 3	XX (XX.X)	XX (XX.X)	XX.X (XX.X - XX.X)	X.XXX	
Other species P. malariae, P. Ovale, P. knowlesi (PCR result only)					
All months	XX (XX.X)	XX (XX.X)	XX.X (XX.X - XX.X)	X.XXX	
Month 1	XX (XX.X)	XX (XX.X)	XX.X (XX.X - XX.X)	X.XXX	
Month 2	XX (XX.X)	XX (XX.X)	XX.X (XX.X - XX.X)	X.XXX	
Month 3	XX (XX.X)	XX (XX.X)	XX.X (XX.X - XX.X)	X.XXX	

# 4.4.2 Quantifying the impact of the ACT artemether-lumefantrine (AL) as prophylaxis for forest goers on overall malaria transmission using mathematical modelling

A transmission dynamic mathematical model will be developed and used to simulate the impact of AL prophylaxis on malaria transmission at a population level.

# 4.4.3 Assessing the impact of artemether-lumefantrine prophylaxis on the spread of genetic markers of artemisinin (such as Kelch13 mutations) and partner drug resistance.

The prevalence of *Kelch13* mutations and other genetic markers of antimalarial drug resistance of known functional significance will be analysed and presented in table 4 below.

Table 4 Day 28 -PCR positivity by resistance markers e.g. Pfkelch	h13 status
---	------------

	Detection of relevant	Detection of relevant Pfkelch13 mutation		
	Yes	No (wild type)	Risk Difference	p-value
	(N=XXX)	(N=XXX)	(95% CI)	
Artemether-	XX.X (X.X)	XX.X (X.X)	XX.X (X.X)	X.XXX
Lumefantrine				
Multivitamin	XX.X (X.X)	XX.X (X.X)	XX.X (X.X)	X.XXX

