4.2. Secondary Objectives

1. To compare the efficacy of the ACT artemether-lumefantrine versus a multivitamin preparation as defined by the 28-day, 56-day and 84-day PCR parasite positivity rate and incidence of confirmed clinical malaria for each species.

2. To quantify the impact of the ACT artemether-lumefantrine as prophylaxis for forest goers on overall malaria transmission using mathematical modelling.
3. To assess the impact of artemether-lumefantrine prophylaxis on the spread of genetic markers of artemisinin (such as *Kelch13* mutations) and partner drug resistance.
4. To obtain data on the place of residence, work, recent travel history and risk behaviours of forest goers in order to improve the understanding of high risk groups, locations of malaria transmission and possible routes spread of malaria and artemisinin resistance.
5. To explore the duration, location and purpose of individual forest visits.
6. To obtain detailed data and GPS mapping on a subset of participants and their peers relating to the behaviours and risk factors associated with malaria infection in order to improve understanding of local malaria transmission among forest goers.
7. To determine the prevalence of asymptomatic *Plasmodium* infections in high risk populations at varying seasonal time points.
8. To determine the prevalence of other infectious diseases that affect the study population

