6.8.2 Parasite genetic analysis

Blood samples (dried blood spots) for parasite genetic analysis will be obtained and stored from all subjects recruited with subject's consent. In individuals in whom parasites are found by PCR, samples will be processed for parasite genetic analysis. Genetic samples (in the form of dried blood spots or extracted DNA) will be stored (for a maximum of 10 years) at the Molecular Tropical Medicine Laboratory, Bangkok, Thailand. In those with confirmed clinical malaria, parasite genotyping will be performed at the Wellcome Trust Sanger Institute in Hinxton, UK or other suitable laboratory using a set of informative single nucleotide polymorphisms selected from whole genome sequencing. The subject will be asked for consent for this transfer during the initial informed consent process. A material transfer agreement will be in place if required before any samples are shipped. The results of the parasite genotyping will not be reported back to the subjects. This analysis will only be done for those with confirmed clinical malaria as it is anticipated that there will be insufficient genetic material in samples taken from those with asymptomatic infection due to the low parasite burden in these individuals.

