#### 2. STUDY OBJECTIVES AND ENDPOINTS

2.1 PRIMARY OBJECTIVE

To compare the efficacy of the ACT artemether-lumefantrine versus a multivitamin preparation as defined by the 28-day **PCR parasite positivity rate or incidence of confirmed clinical malaria** of any species.

- 2.2 PRIMARY ENDPOINT
  - The 28-day PCR Plasmodium positivity rate of any species or
  - Proportion of participants with **confirmed clinical malaria** of any species reported between day 0 and day 28, at any and each of the Month 1, Month 2 or 3 follow-ups.
- 2.3 SECONDARY OBJECTIVES AND ENDPOINTS

This section outlines the secondary objectives and the corresponding endpoints. A detailed plan for analysis of some of these endpoints will be produced the specialised groups as shown below:

• To compare the efficacy of the ACT artemether-lumefantrine (AL) versus a multivitamin preparation as defined by the 28-day, 56-day and 84-day PCR parasite positivity rate or incidence of confirmed clinical malaria for each species.

Composite endpoint

- 28-day, 56-day and 84-day PCR Plasmodium positivity rate for each Plasmodium species or
- Proportion of participants with confirmed malaria reported between day 0 and day 28 for each species
- To quantify the impact of the ACT artemether-lumefantrine (AL) as prophylaxis for forest goers on overall malaria transmission using mathematical modelling.

 To assess the impact of artemether-lumefantrine prophylaxis (AL) on the spread of genetic markers of artemisinin (such as Kelch13 mutations) and partner drug resistance.
 Endpoint

- Prevalence of Kelch13 mutations and other genetic markers of antimalarial drug resistance of known functional significance

 To obtain data on the place of residence, work, recent travel history and risk behaviours of forest goers in order to improve the understanding of high risk groups, locations of malaria transmission and possible routes of spread of malaria and artemisinin resistance.
 Endpoint

- Data on the place of residence, work, recent travel history and mobile phone use events covering the whole population during the course of prophylaxis.

 To obtain detailed data and GPS mapping on a subset of participants and their peers relating to the behaviours and risk factors associated with malaria infection in order to improve understanding of local malaria transmission among forest goers.
 Endpoint

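### SAP Table 4 contrasts mutant with wild type within each arm, so the resistance objective has no specified AL v multivitamin comparison of marker prevalence

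*SAP*

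**What the plan says.** **Objective and endpoint.** Protocol 4.2 sets the aim "To assess the impact of artemether-lumefantrine prophylaxis on the spread of genetic markers of artemisinin" and partner-drug resistance, and SAP 2.3 repeats it. The endpoint listed under it in SAP 2.3 is "Prevalence of Kelch13 mutations and other genetic markers of antimalarial drug resistance of known functional significance".

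**Analysis.** SAP 4.4.3 says that this prevalence "will be analysed and presented in table 4 below". Table 4 is then titled "Day 28 -PCR positivity by resistance markers", with Pfkelch13 as the example. Its main header, "Detection of relevant Pfkelch13 mutation", splits into Yes and No (wild type), followed by a risk difference with 95% CI and a p-value. The two arms are the rows, so each arm has its own risk difference and its own p-value.

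**Who is genotyped.** Protocol 6.8.2 says "In individuals in whom parasites are found by PCR, samples will be processed for parasite genetic analysis". Later in the same section, after describing SNP genotyping at an external laboratory, it says "This analysis will only be done for those with confirmed clinical malaria", because asymptomatic infections are expected to yield too little material. Protocol 6.6.3 and the schedule in Appendix 1 tie the genetic sample to episodes of confirmed clinical malaria. Protocol 6.6 lists it among follow-up samples for people who had such an episode. The SAP does not say which sample defines Kelch13 status.

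**The concern.** The objective asks what AL does to resistance markers, and randomisation allows that to be answered by comparing the arms. Table 4 attaches its inference to a different comparison: mutant against wild type inside one arm. Someone programming the shell as it stands would place within-arm p-values under a heading about the impact of AL, and readers could take them as evidence for or against selection of resistance. The title also names an outcome, PCR positivity, that is not the endpoint.

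This goes beyond missing detail. Tables 2, 3, 5 and 6a of the same SAP have the arms in columns; Table 4 turns the layout round and puts the test on the other axis.

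**Working it through.** **1. What Table 4 tests, by source of the genotype**

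| Kelch13 status or cell content | What the cells hold | What each row's p-value tests |
|---|---|---|
| Status from day-28 PCR-positive samples | 100% in both columns, because a genotype needs parasites | Nothing: difference 0 |
| Status from a clinical-episode (or baseline) sample | Day-28 positivity, which can be below 100%, for example after treatment | Mutant v wild type within one arm |
| Cells read as row percentages (share mutant, share wild type) | p and 1 - p | Whether 2p - 1 = 0, that is, whether prevalence is 50% |

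Invented counts show each row of this table:
- Day-28 samples: 46/46 v 20/20 on AL and 55/55 v 55/55 on multivitamin both give a difference of 0 and Fisher p = 1. A chi-squared test is undefined.
- Clinical-episode samples: 5/20 v 2/15 in one arm is 25% v 13%, Fisher p = 0.67. The cells are not fixed, but the multivitamin arm plays no part in the result.
- Row percentages: 46/66 mutant gives 69.7% - 30.3% = 39.4 points, and 55/110 gives 0. Neither is a difference between arms.

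**2. The plan's own figure, used to size the number of infections**

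Inputs from SAP 2.5: *P. falciparum* (Pf) positivity 5% v 3%, 80% power, 5% significance, 1,605 episodes per arm before inflation and 2,200 after. The two-sided normal-approximation formula for two proportions gives n0 = 1,506. With the continuity correction, n = (n0/4) x [1 + sqrt(1 + 4/(n0 x 0.02))]^2 = 1,605, which reproduces the plan.

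Expected Pf-positive episodes:
- At 2,200 per arm: 0.05 x 2,200 = 110 on multivitamin and 0.03 x 2,200 = 66 on AL.
- At 1,605 per arm: about 80 and 48.

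**3. What a between-arm comparison could show**

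The documents give neither a Kelch13 prevalence nor the share of infections that will be genotyped, so both are assumptions here. Power for a 20-point higher mutant share on AL, two-sided 5%, ignoring clustering, starting from 110 v 66:

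| Share genotyped | Infections (multivitamin v AL) | Prevalence 30% on multivitamin | 50% | 70% |
|---|---|---|---|---|
| All | 110 v 66 | 76% | 75% | 90% |
| Half | 55 v 33 | 47% | 45% | 60% |
| One fifth | 22 v 13 | 22% | 20% | 25% |

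These shares only indicate scale. Clinical cases need not be a subset of day-28 positives.

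**4. Why the denominator must be stated**

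Invented example: 46 of 66 infections mutant on AL, 55 of 110 on multivitamin. Intervals are Wald, d +/- 1.96 x SE, without clustering.
- Among infections: 46/66 - 55/110 = 69.7% - 50.0% = +19.7 points; SE = sqrt(0.697 x 0.303/66 + 0.5 x 0.5/110) = 0.074; 95% CI 5.2 to 34.2; Fisher p = 0.012.
- Mutant infections per randomised episode: 46/2,200 - 55/2,200 = 2.09% - 2.50% = -0.41 points; 95% CI -1.29 to 0.48.
- Wild-type infections per randomised episode: 20/2,200 - 55/2,200 = 0.91% - 2.50% = -1.59 points.

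Here AL raises the mutant share by preventing wild-type infections, while the number of mutant infections is slightly lower. The two denominators answer different questions and have opposite signs.

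**The case against.** **The shell is illustrative and the text governs.** SAP 4.4.3 does say that prevalence will be analysed, and both arms appear in the table, so counts in the cells would let a reader work out prevalence by arm. That stands as far as description goes. The only difference and p-value planned, however, still run across genotype within an arm.

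**Column percentages.** The N sits at the head of each genotype column. Read that way, the AL row compares AL's share of mutant infections with its share of wild-type infections. In the example this is 46/101 - 20/75 = 45.5% - 26.7% = 18.9 points, which does test the association between arm and genotype. But the multivitamin row would be its mirror image, the result is not marker prevalence, and nothing in the title or text points to this reading.

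**Cover elsewhere.** SAP 2.3 allows specialised groups to write detailed plans for some endpoints, and Protocol 9.2.1 gives a general chi-squared or Fisher rule for proportions. Neither names the resistance comparison, its sample or its denominator.

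**Protocol 6.8.2 may describe two steps.** PCR-positive samples could be processed in one way and SNP genotyping kept for clinical cases. That is a fair reading, and it means that a clarification may be enough. It still leaves open which infections enter Table 4.

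**A stronger reading is tempting.** A reader might infer that Table 4 is 100% v 100% by construction and that the missing comparison follows from this. The documents do not support either step. The 100% cells need Kelch13 status to come from the day-28 positive sample, which the SAP does not say; Protocol 6.6, 6.6.3, 6.8.2 and Appendix 1 point mainly to clinical episodes, and a treated case can be PCR-negative at day 28. The missing comparison follows from the layout, whatever the cells hold.

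**Conclusion.** The point holds in this form: Table 4's title does not match the prevalence endpoint, its risk differences and p-values are laid out within arm, and the SAP specifies no AL v multivitamin comparison of markers. Degenerate cells (difference 0, Fisher p = 1) are one possible outcome, conditional on using day-28 samples.

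This is one of eight secondary objectives and leaves the primary analysis untouched, but the objective cannot be answered from the table as drawn. The layout finding needs no numerical assumption. The 110 v 66 infections rest on the plan's 5% and 3% Pf rates with all 2,200 episodes per arm contributing. The mutant counts, marker prevalences and genotyped shares are illustrative. If only a minority of infections are genotyped, power will be low, so the comparison should be presented as an estimate with its interval.

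**What to change.** In SAP 4.4.3:

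1. Make AL and multivitamin the columns of Table 4, and retitle it for marker prevalence.
2. Report the between-arm difference in marker prevalence among genotyped infections, with a 95% CI. This is the stated endpoint; flag that it conditions on infection, which occurs after randomisation.
3. Alongside it, report the between-arm differences in mutant and in wild-type infections per randomised episode, noting that infections without a genotype are not counted in either row. Which of the two denominators leads is a choice for the sponsor; it should be fixed before genotypes are seen by arm.
4. Allow for repeat episodes from the same participant in every interval, for example with the robust standard error that SAP 4.3 already uses.
5. State which sample (baseline, clinical episode, or day 28, 56 or 84) defines Kelch13 status, and show the number genotyped out of the number eligible in each arm.

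In Protocol 6.8.2, reconcile the two statements on who is genotyped, so that one population is named and matches the table.

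The cost is a redrawn table shell, a few sentences of SAP text and a clarification in the protocol. No new samples are needed if the existing ones are used.
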